## Statistical Analysis

Our primary hypothesis is that vibrotactile CR stimulation (i) will improve the outcome measured as On-time at least by 30% compared to the baseline after three months of usage. We also expect that (ii) the relative increase in On-time in the intervention arm (using vibrotactile CR stimulation) will be at least 20% compared to the control arm (Sham) after three months of usage. In order to test these hypotheses, we will perform Welch's t-test (paired t-test for the first hypothesis and unpaired two-sample t-test for the second hypothesis). Our power analysis shows that the sample size of 10 patients for each arm will provide 85% - 98% of power for detecting statistically significant difference based on the mean On Time of 7.3 at baseline and SD of 2-2.5 that were obtained from our preliminary study.

**Based on this power analysis, we are planning to enroll a minimum of 60 patients. 30 patients will be randomized to receive the real stimulation initially. The remaining 30 will be randomized to receive sham stimulation, using dedicated sham stimulation pattern.**

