Based on this study, we propose to deliver vibrotactile CR stimulation during a longer treatment period, in order to assess durability and efficacy vs. a sham vibrotactile approach. This study is designed to best assess vibrotactile CR stimulation compared to sham as an alternative to best medical therapy for Parkinson's disease. With our

project, we are hoping to establish a simple, non-invasive treatment that will provide ongoing relief with minimal side effects or inconvenience to the patient.

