#### Sham control

Parkinson's patients are particularly vulnerable to the placebo effect. The best method of reducing placebo effects in a placebo effect prone population is to blind the participants. In order to do this, sham participants will receive a non-stimulation (0 amplitude) chip that is inserted into the vibrotactile device. All participants will be told that they will receive 1 of two chips, 1 is regular vibrotactile reset and the other (sham) is called Stochastic resonance vibrotactile coordinated reset. The patient will learn that Stochastic resonance treatment is most effective when the patients vibratory stimulus threshold (i.e the minimum perception thresholds) is set as 90%. This means that the patient should not feel the vibrations on their fingers if they receive vibratory stochastic resonance. We will take vibrotactile threshold measurements from patients to make this story convincing and to add another dependent measure. If placed into the sham condition, the patient will receive no stimulation, however they will be convinced that they are receiving stimulation

Vibrotactile CR stimulation therapy system is a commercially available (though not yet FDA-approved), non-invasive, battery-operated mobile device. The device consists of a handheld component with vibro-tactile stimulators (tactors) and is fitted and programmed by a qualified healthcare professional familiar with Parkinson's disease treatment (e.g., physicians, advanced practice providers, nurses and/or their clinical research assistants).

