#### Primary Hypothesis

Vibrotactile CR stimulation is not expected to cause discomfort or pain in patients as confirmed in a prior study with Parkinson's disease (IRB# 45096; Syrkin-Nikolau et al., 2018). It is expected to lead to a decrease in severity of motor symptoms from baseline to 6 months, as measured by the Movement Disorders Society's Unified Parkinson's Disease Rating scale (MDS-UPDRS) part III and patient motor diaries to capture mean time when patients' medications have worn off and are not controlling symptoms (OFF time), time when patients' medications are working effectively to control symptoms (ON time), ON time with troublesome dyskinesia, and sleep time – all factors which can be affected by Parkinson's disease. As secondary endpoints, we expect this may result in the patient's ability to reduce reliance upon dopaminergic medications, therefore we will measure changes in levodopa dose equivalency. Additionally, we will assess for improvement in non-motor symptoms of Parkinson's disease, ability to perform activities of daily living and reduction in dyskinesia, which will be measured by the Movement Disorders Society's Unified Parkinson's Disease Rating scale (MDS-UPDRS), parts 1, 2 and 4 and the Schwab and England Activities of Daily Living score. We expect patient quality of life will increase after stimulation, which will be measured by the Parkinson's Disease Questionnaire-39 (PDQ-39) scale. To get a general sense of symptom change, we will assess the patient and clinician Global Rating of Change (GRC) scale and the Patient Global Impression of Change. We will also asses speech using comprehensive speech evaluations. We predict that this decrease in symptoms will be apparent within 1 month of vibrotactile stimulation and that this treatment will be durable as assessed up to 1-months post-stimulation.

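### The lead primary hypothesis is a before-after test in the active arm, with no success rule and no requirement that the sham comparison succeed, so placebo response could satisfy it

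*Combined protocol and SAP*

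**What the plan says.** The Statistical Analysis section states as primary that vibrotactile CR stimulation "will improve the outcome measured as On-time at least by 30% compared to the baseline after three months of usage". It continues: "We also expect that (ii) the relative increase in On-time in the intervention arm" will be at least 20% relative to sham, also at three months. The tests are a "paired t-test for the first hypothesis and unpaired two-sample t-test for the second hypothesis". The section then claims 85%-98% "of power for detecting statistically significant difference based on the mean On Time of 7.3 at baseline", with an SD of 2-2.5 and 10 patients per arm, and plans at least 60 patients, 30 per arm. It gives no alpha, sidedness, order of testing or rule for calling the trial positive.

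The Primary Hypothesis section is also worded as change over time, a "decrease in severity of motor symptoms from baseline to 6 months", and does not mention sham. The Background, by contrast, says the study is "designed to best assess vibrotactile CR stimulation compared to sham", and the Sham control section says that people with Parkinson's disease "are particularly vulnerable to the placebo effect".

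**The concern.** Only the active arm receives CR stimulation, so hypothesis (i) is a before-after comparison within that arm. Placebo response, regression to the mean and changes in concomitant medication all enter its result in full. The sham arm was set up to remove these influences, and (i) makes no use of it.

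Two rules are missing. The first is how (i) and (ii) combine: nothing prevents the primary hypothesis from being declared met on (i) when (ii) fails. The second is what counts as meeting (i). It could mean rejecting zero change, rejecting zero change with an observed gain of at least 30%, or rejecting a gain of 30% or less. The power sentence speaks of detecting a significant difference, which points to the first reading. Under that reading an inert device can meet the primary hypothesis while the arms do not differ. A t-test against zero also does not by itself show a gain of at least 30% or a difference of at least 20%.

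**Working it through.** **Inputs from the Statistical Analysis section.** Baseline mean On-time 7.3 (unit not stated; taken as hours); SD 2-2.5; 10 per arm for the power claim; 30 per arm planned; effects of 30% and 20%.

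**Assumptions.** Two-sided alpha 0.05 unless stated; SD 2-2.5 is the SD of the change; 20% in (ii) means 20% of baseline; an inert device gives the same placebo gain in both arms, 10% or 20% of baseline. The documents give no size for the placebo response.

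**Effects in hours.** 30%: 0.30 × 7.3 = 2.19. 20%: 0.20 × 7.3 = 1.46. 10%: 0.10 × 7.3 = 0.73.

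**1. The plan's own power figure (n = 10 per arm).**

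| Test | SD 2 | SD 2.5 |
|---|---|---|
| (i) paired t, two-sided, 2.19 h | 86.8% | 69.4% |
| (i) paired t, one-sided, 2.19 h | 93.8% | 81.8% |
| (i) normal approximation, one-sided, Φ(2.19√10/SD − 1.645) | 96.5% | 87.0% |
| (ii) two-sample t, two-sided, 1.46 h | 34% | 23% |

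Only the one-sided normal approximation for (i) comes within two points of 98% and 85%. For (ii), even the most favourable reading tried (20% of 9.49 h = 1.90 h, one-sided normal) gives 68% and 52%. The stated power therefore fits the within-arm test and not the sham comparison.

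**2. Inert device, n = 30, success on (i) means rejecting zero change.** Power comes from the noncentral t with 29 df and noncentrality gain × √30/SD. The joint result is from simulation of the paired and the two-sample test.

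| Shared gain | (i) significant, SD 2 / 2.5 | (i) significant and (ii) not, SD 2 / 2.5 |
|---|---|---|
| 0.73 h | 48.9% / 34.0% | 46.4% / 31.5% |
| 1.46 h | 97.1% / 87.1% | 92.9% / 83.8% |

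Test (ii) rejects in 5.0% of trials throughout, and in favour of CR in about 2.5%.

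**3. Same device, observed gain of at least 2.19 h also required.** The probability is 1 − Φ((2.19 − gain)√30/SD). At 0.73 h it is 0.003% (SD 2) or 0.07% (SD 2.5); at 1.46 h it is 2.3% or 5.5%. A device with a true gain of exactly 2.19 h passes 50% of the time. That does not fit 85%-98% power unless a larger true gain was assumed.

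**4. What a significant result would show at n = 30.**
- For (i), the smallest significant change is t(0.975, 29) × SD/√30 = 2.045 × SD/5.477 = 0.75-0.93 h, or 10%-13% of 7.3 h.
- For (ii), the smallest significant difference is t(0.975, 58) × SD × √(2/30) = 2.002 × SD × 0.258 = 1.03-1.29 h, or 14%-18% of 7.3 h.

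Both lie below the 30% and 20% named in the hypotheses.

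**The case against.** The strongest reply is that the plan says at least 30% and nowhere says that rejecting zero is enough. If the 30% is enforced on the observed gain, the placebo risk is small (step 3). If it is the null value, an inert device with a 20% gain rejects in at most about 0.02% of trials. This stands as a limit: the high false-success figures belong to one reading. But the plan does not choose a reading, its power sentence favours the zero null, and none of the three readings of (i) uses sham data.

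The sham comparison is also a planned test, numbered alongside (i), and will be reported. That is correct. What is missing is its rank and its role in the conclusion.

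The size of the problem rests on assumed inputs. At a 5% shared gain (0.365 h), (i) succeeds in only 12%-16% of trials. If 2-2.5 is the SD of On-time itself, the SD of change is SD × √(2(1 − r)), and for correlations r of 0.3 to 0.8 the 10%-gain result runs from 26% to 86%. The direction does not change: any shared gain inflates (i) and leaves (ii) unaffected.

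Finally, the Benefits section calls this a pilot, and requiring both hypotheses, or testing (ii) first, would also close the gap. But that same section says the study could provide evidence of a safe and effective method, and the plan states formal tests with power. The change-from-baseline wording in the Primary Hypothesis section is ordinary and does not exclude an arm comparison, so it is supporting evidence only.

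**Conclusion.** The concern holds, and the plan must be changed before it can support an efficacy conclusion. The lead primary test cannot separate device effect from placebo response, and no rule makes the claim depend on the comparison with sham that the study was designed to make. If rejecting zero is success, an inert device meets (i) in about one third to one half of trials at a shared 10% gain, and in 87%-97% at 20%. In most of those trials (ii) is not significant. These rates assume 30 per arm, two-sided 5%, SD of change 2-2.5, and a placebo gain that the documents do not quantify. The absence of a success rule and of a ranking depends on none of these assumptions.

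**What to change.** In the Statistical Analysis section, make the active-minus-sham difference in On-time at three months the single confirmatory test (null: no difference, two-sided 0.05), and report the estimate with its 95% CI. Report within-arm changes descriptively for both arms. Describe 30% and 20% as expected effects and state the base of the 20%. Word the Primary Hypothesis section as a comparison with sham. Restate the power for the between-arm test.

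This is a change of wording with no new data collection. The cost is that the sponsor gives up the easier test. For a difference of 1.46 h, two-sided power is 60%-79% at 30 per arm and 23%-34% at 10 per arm (SD 2.5 and 2). Reaching 80% takes 31 (SD 2) to 48 (SD 2.5) per arm, so the sponsor either accepts lower power or enrolls above the stated minimum of 60, which the plan already permits. If 20% instead means 20% of sham On-time after a 10%-20% sham gain (0.2 × 8.03 = 1.61 h to 0.2 × 8.76 = 1.75 h), power at 30 per arm is 69%-92%.

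### The plan does not say how the relative increase in On-time is derived for the sham comparison; if averaged from per-patient percentages, it shows a gain when nothing changes and has less power than baseline-adjusted hours

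*Combined protocol and SAP*

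**What the plan says.** The Statistical Analysis section sets two expectations for On-time at three months. Hypothesis (i) is within the active arm: stimulation "will improve the outcome measured as On-time at least by 30% compared to the baseline after three months of usage". Hypothesis (ii) is the randomised comparison: "the relative increase in On-time in the intervention arm (using vibrotactile CR stimulation) will be at least 20% compared to the control arm (Sham", again at three months. The tests are given as "paired t-test for the first hypothesis and unpaired two-sample t-test for the second hypothesis", under the general label of Welch's test.

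The only numerical inputs are the "mean On Time of 7.3 at baseline and SD of 2-2.5 that were obtained from our preliminary study". The power statement is that "the sample size of 10 patients for each arm will provide 85% - 98% of power", and enrolment is then set at a minimum of 60, 30 per arm.

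The section does not define the relative increase. It could be a mean of individual ratios, a ratio of arm means, or just the effect size assumed for a test on hours. No baseline adjustment, significance level or sidedness is stated.

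**The concern.** A two-sample t-test needs one value per patient. An analyst told to compare the relative increase between arms could reasonably compute each patient's percent change from baseline and test that. The plan does not rule this out.

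The mean of individual percentages is not the percentage change of the mean. A low baseline inflates a patient's percentage more than an equally high baseline deflates it, so the average drifts upward with no real change. The ratio is also skewed and widely spread, which can cost power in the only randomised comparison. At stake are the size of the reported gains and the trial's ability to separate the device from sham.

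**Working it through.** **Inputs from the Statistical Analysis section.** Mean On-time 7.3 (taken as hours); SD 2 to 2.5; 30 per arm. So CV = 2/7.3 = 0.274 to 2.5/7.3 = 0.342, and CV² = 0.075 to 0.117. The targets in hours are 0.30 × 7.3 = 2.19 h and 0.20 × 7.3 = 1.46 h.

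**Assumptions (not in the plan).** Two-sided 5% level; same SD at month 3; baseline to month-3 correlation ρ = 0.5 (range 0.3-0.8); On-time normal with a 1 h or 3 h floor, bounded, or log-normal; no dropout.

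**1. The plan's own power figure.** For (ii), a 1.46 h difference with 10 per arm gives 34% (SD 2) and 23.5% (SD 2.5) by two-sided t-test, not 85-98%. With 30 per arm it gives 79% and 60%. The stated range is approached only for (i), as a one-sided normal calculation with 2-2.5 used as the SD of change:
- SD 2: 2.19/2 × √10 − 1.645 = 1.82, power 96.5%.
- SD 2.5: 2.19/2.5 × √10 − 1.645 = 1.13, power 87.0%.

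These inputs are in units of On-time, so the stated power does not describe a test of ratios.

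**2. Two patients.** One goes from 4 to 7 h (+75%), another from 7 to 4 h (−43%). Total On-time is unchanged, but the mean percentage is (75 − 43)/2 = +16%.

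**3. Mean percentage under no change.** Approximately CV² × (1 − ρ). At ρ = 0.5 this is 0.075 × 0.5 = 3.8% (SD 2) and 0.117 × 0.5 = 5.9% (SD 2.5). Simulation with a normal distribution and a 1 h floor gives 5.2% and 9.6%, because very low baselines weigh more than the approximation allows. Over ρ = 0.3-0.8 and the several distributions the range is about +1% to +14%. The ratio of arm means shows about 0.

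**4. Difference from sham.** If the benefit is a fixed number of hours, the true 20 points read as roughly 20 × (1 + CV²): 20 × 1.075 = 21.5 and 20 × 1.117 = 22.3. If the benefit is proportional, they read as roughly 20 × (1 + CV²(1 − ρ)): 20 × 1.038 = 20.8 and 20 × 1.059 = 21.2. Simulations give about 20-24. The between-arm type I error of the ratio test stays at about 4-5%.

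**5. Power against sham** (30 per arm, ρ = 0.5, true gains of 30% active and 10% sham, fixed hours):

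| On-time model | SD | Percent change | Change in hours | Loss (points) |
|---|---|---|---|---|
| Normal, 1 h floor | 2 | 56% | 80% | 24 |
| Normal, 1 h floor | 2.5 | 34% | 61% | 27 |
| Normal, 3 h floor | 2 | 63% | 79% | 16 |
| Normal, 3 h floor | 2.5 | 45% | 61% | 16 |
| Log-normal | 2 | 73% | 78% | 5 |
| Log-normal | 2.5 | 57% | 61% | 4 |

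With a 20% gain and none on sham, the loss is about 11-18 points in near-normal or bounded models. In the log-normal model it is about nil, or reversed by up to 3 points. Month-3 hours adjusted for baseline (ANCOVA) give about 88-89% (SD 2) and 72-73% (SD 2.5), above percent change in every scenario tried at ρ = 0.5.

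**6. Higher correlation.** At ρ = 0.7, SD 2, with a 20% gain, none on sham and near-normal On-time, power is 88% for percent change, 80% for unadjusted month-3 hours, 94% for change in hours and 97% for ANCOVA.

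**The case against.** The strongest reply is that the plan never says a ratio is formed per patient. It states an expectation for the arm, and its power inputs are for On-time itself. A t-test on hours, with 20% as the planning effect, fits the text at least as well. This stands. The documents do not support a statement that the plan's derived value is wrong, only that it is undefined and that one natural reading performs poorly.

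Three further inferences are tempting and do not hold.

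- **The 30% target would be reached too easily.** Under per-patient averaging, a true 25% gain would read as 30% or more in about 60% (SD 2) to 76% (SD 2.5) of trials at ρ = 0.5. But the 30% belongs to hypothesis (i), which has a paired t-test. That test takes hours directly and its mean difference is unbiased. The inflation arises only if the within-arm percentage is also averaged per patient, which the plan does not say.
- **The device would falsely beat sham.** Most of the bias is common to both arms and the type I error is not inflated.
- **Percent change is weaker than any test on hours.** It can beat an unadjusted test of month-3 hours when the correlation is 0.7 or more, and its loss against change in hours depends on a distribution and a sham gain that the plan does not give.

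**Conclusion.** The point holds in conditional form. The quantity compared with sham is undefined. If it is taken as per-patient percent change, its mean is biased upward in each arm, by about 4 to 10 percentage points under no change at ρ = 0.5. The effect on the between-arm difference is small, at most about 4 points on a true 20. The more important consequence is power: near-normal On-time with gains of 30% and 10% costs 15-27 points against change in hours, and log-normal On-time costs 4-6. Baseline-adjusted hours did better in every scenario at that correlation.

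The direction of the bias follows from the arithmetic of ratios and from the plan's own mean and SD. The sizes rest on an assumed correlation, distribution and significance level. The matter is worth correcting because it concerns the only randomised comparison and costs almost nothing to settle.

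**What to change.** In the Statistical Analysis section, state that:

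1. Hypothesis (i) is tested by the paired t-test on On-time in hours.
2. Hypothesis (ii) compares month-3 On-time in hours between arms, adjusted for baseline On-time by ANCOVA. If an unadjusted test is preferred, name change in hours as the outcome. Per-patient percent change is not used for either test.
3. The 30% and 20% figures are reported from arm means: (mean month-3 On-time / mean baseline On-time) − 1 in each arm, and the active-minus-sham difference in that quantity, each with an interval (a bootstrap interval would serve).
4. The planning equivalents are 2.19 h and 1.46 h. They match the percentages only at a baseline mean of 7.3 h.

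The cost is a few sentences. It needs no more patients or visits, and only the baseline On-time that (i) already requires. The one drawback for the sponsor is that reported percentage gains will be a few points less favourable than averaged individual percentages.

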## Protocol summary

### **Day 0: Baseline testing (screening):**

- Patient medical history
- General physical exam
- Neurological exam
- Concomitant and PD medications (Levodopa equivalents in mg)
- OFF MDS-UPDRS, part III 12 hour washout of short-acting and 24 hour washout of long acting levodopa containing medications)
- ON MDS-UPDRS, part III (1-2 hours after taking levodopa)
- MOCA and SCOPA
- Clinically trained staff (MD, PA, or RN) will review the consent form in detail with the participant and answer any questions about the study. After consent, the participant will be enrolled in the study and randomized to CR or sham.

- Blinding form – patient
- Blinding form – assessing clinician (MD, PA, RN)

*Surveys to be completed after accepted into study and prior to the 1st day of enrollment. Survey will be completed on medication and sent via email*

1. MDS-UPDRS, Parts I-II, and IV
2. Parkinson's Disease Questionnaire-39 (PDQ-39) scale
3. Schwab and England Activities of daily living score
5. Beck depression and Anxiety inventory

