**Day 1: 1-2 weeks after baseline screening**

- Off Medication UPDRS
- Randomization to CR vs Sham vibrotactile stimulation
- Vibrotactile threshold measurements
- EEG recordings to assess PD-related brain oscillation
- Smell Test
- Comprehensive speech evaluation

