**Day 2**

- Off medication UPDRS
- In-clinic, wearable accelerometer/gyroscope (Kinesia One; ambulatory parkinsons disease monitoring (APDM)) to capture tremor and gait
- •Patient does stimulation for 2 x2 hours with a break in between
- •Repeat UPDRS part III to asses acute CR treatment
- •Repeat In-clinic, wearable accelerometer/gyroscope (Kinesia One; APDM) to capture tremor and gait

Weekly Phone Call to assess AE's, review diary and change in medications

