**Month 1- month 6 (daily, at home):**

- 2hr vibrotactile stimulation (CR vs sham), Session 1 morning
- 2hr vibrotactile stimulation (CR vs sham), Session 2 late afternoon
- Hauser diary to capture OFF time, ON time, ON time with troublesome dyskinesia, sleep time

Patients will return **at 3, 6 and 7 months** and will follow the same procedures as enrollment day 1 and 2

[figure not shown]
After the 6 month follow up, the patient will receive no stimulation for 1 month to asses long term effects and return at 7 months for a follow up assessment.

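### The CR-versus-sham test of month-3 On-time is valid but uses baseline On-time inefficiently; pre-specifying ANCOVA is a low-cost gain, of a size that depends on a correlation the plan does not give

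*Combined protocol and SAP*

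**What the plan says.** The Statistical Analysis section is the only analysis text. Hypothesis (i) is a within-arm rise in On-time of at least 30% over baseline at three months. Hypothesis (ii), the only randomised On-time comparison, is that "the relative increase in On-time in the intervention arm (using vibrotactile CR stimulation) will be at least 20% compared to the control arm (Sham", also at three months. The tests are a "paired t-test for the first hypothesis and unpaired two-sample t-test for the second hypothesis". No covariate, model or stratification factor is named. The power statement is "based on the mean On Time of 7.3 at baseline and SD of 2-2.5". It gives no correlation between baseline and follow-up, no alpha and no dropout rate. At least 60 patients are planned, 30 per arm.

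A baseline On-time is presupposed. Hypothesis (i) needs one, and the Primary Hypothesis section states, with motor diaries among the measures: "It is expected to lead to a decrease in severity of motor symptoms from baseline to 6 months".

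In the Protocol summary, the weekly call listed after the Day 2 procedures is to "review diary and change in medications", and the at-home block for months 1 to 6 lists a "Hauser diary to capture OFF time, ON time, ON time with troublesome dyskinesia, sleep time". The Data collection section describes an electronic motor diary on a wearable instead. Randomisation appears twice: under Day 0 ("After consent, the participant will be enrolled in the study and randomized to CR or sham") and under Day 1 ("Randomization to CR vs Sham vibrotactile stimulation").

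**The concern.** Baseline On-time usually predicts later On-time. A two-sample t-test on month-3 hours ignores it. A t-test on change uses it with a fixed weight of one, which is too much when the correlation is modest. ANCOVA estimates the weight from the data. The plan needs the baseline value anyway, so leaving it out of the randomised comparison, or using it with the wrong weight, gives up power without saving effort.

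The wording of hypothesis (ii) also leaves the tested variable open. The candidates differ in power, so the variable should be fixed before the data are seen. What is at stake is the precision of the one comparison that the sham arm exists to support, not its validity.

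**Working it through.** **Inputs from the Statistical Analysis section.** Baseline mean 7.3 (taken as hours), SD 2 to 2.5, 30 per arm, 20% between arms, 30% within arm.

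**Assumptions.** Two-sided 5%, no dropout, SD 2 to 2.5 h is the SD of On-time at each time point, and ρ (baseline to month-3 correlation) is 0.3, 0.5 or 0.7. The documents give no ρ.

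**The plan's own figure.** It states 85% to 98% power with 10 per arm, without saying for which hypothesis.
- Hypothesis (ii), 10 per arm, 1.46 h: 34% (SD 2) and 24% (SD 2.5).
- Hypothesis (i), n = 10, 30% × 7.3 = 2.19 h, SD read as the SD of change: 87% and 69% two-sided. A one-sided normal approximation gives 96.5% and 87.0%.

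The stated range is approached only by the last variant, so it should not be read as the power for CR versus sham.

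**Size of the target.** The 20% can be read in several ways:
- 20% × 7.3 = 1.46 h.
- With CR at 1.3 × 7.3 = 9.49 h and sham at 9.49/1.2 = 7.91 h: 1.58 h.
- 20% × 9.49 = 1.90 h.

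**Formulas.** Power comes from the noncentral t with noncentrality δ / (s√(2/n)), where s is:
- month-3 hours: SD, df 2n − 2
- change: SD√(2(1 − ρ)), df 2n − 2
- ANCOVA: SD√(1 − ρ²), df 2n − 3

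Example, SD 2, ρ 0.5, n = 30. Month-3 hours: 2 × √(2/30) = 0.516, 1.46/0.516 = 2.83, power 79.4%. ANCOVA: s = 2 × √0.75 = 1.732, standard error 0.447, 1.46/0.447 = 3.26, power 89.4%.

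**Results for 1.46 h, 30 per arm (power %, SD 2 / SD 2.5)**

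| ρ | t-test, month-3 hours | t-test, change | ANCOVA | ANCOVA gain over month-3 hours | ANCOVA gain over change |
|---|---|---|---|---|---|
| 0.3 | 79.4 / 60.4 | 65.2 / 46.8 | 83.0 / 64.5 | about 4 | about 18 |
| 0.5 | 79.4 / 60.4 | 79.4 / 60.4 | 89.4 / 72.8 | 10 to 12 | 10 to 12 |
| 0.7 | 79.4 / 60.4 | 94.8 / 81.9 | 97.3 / 87.6 | 18 to 27 | 2.5 to 6 |

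The variance ratios show why the two gains move in opposite directions: 1 − ρ² against month-3 hours, (1 + ρ)/2 against change.

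**No information in baseline.** At ρ = 0, with a variance factor of 1 + 1/56 for chance imbalance, ANCOVA has 78.7 / 59.6 against 79.4 / 60.4, a loss of under 1 point.

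**Check by simulation.** At ρ 0.5 with 8,000 runs, type I error is about 5% for both methods. At 1.46 h, power is 78% / 60% for Welch on month-3 hours and 89% / 72% for ANCOVA.

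**Other readings**
- 1.58 h: month-3 hours 85 / 67; ANCOVA at ρ 0.5, 94 / 79.
- 1.90 h: month-3 hours 95 / 82; ANCOVA 97 / 86 at ρ 0.3 and 99 / 92 at ρ 0.5.
- SD 2 to 2.5 h is the SD of change (1.46 h): change 79 / 60 at any ρ; ANCOVA 93 / 79, 89 / 73 and 85 / 67 at ρ 0.3, 0.5 and 0.7.
- Assumed dropout to 24 per arm (1.46 h, ρ 0.5): month-3 hours 69.7 / 50.8, ANCOVA 81.5 / 62.8, a gain of about 12 points at either SD.
- Percent change was not computed, because it depends on a baseline distribution that the documents do not give.

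**Precision.** At ρ 0.5 the 95% CI half-width falls from 1.03 to 0.90 h (SD 2) or from 1.29 to 1.12 h (SD 2.5). In sample-size terms, 30/(1 − 0.25) = 40 per arm.

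**The case against.** The strongest reply is that nothing is broken. The Welch test is valid under randomisation, the Benefits section calls this a pilot, 60 is a minimum, and hypothesis (ii) may already mean a change score that uses baseline. All of that stands, and it limits the point to efficiency. It does not remove it: ANCOVA also improves on the change score, and the variable still has to be named.

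Four stronger readings are tempting and are not supported.
- **That the gain always grows with the correlation.** This holds only against month-3 hours. Against change it shrinks.
- **That dropout makes the gain larger.** At SD 2.5 it is 12.4 points at 30 per arm and 12.0 at 24.
- **That the comparison is clearly underpowered without adjustment.** On the 1.90 h reading, the t-test on month-3 hours already has 95% / 82%.
- **That no baseline diary is planned.** None is visible in the available schedule text. However, figures are missing from it, the numbered survey list under Day 0 skips item 4, and two sections presuppose a baseline value.

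It is also fair to say that the cost is not trivial on every reading of the schedule. If randomisation is on Day 0, there is no interval between consent and randomisation in which to collect a diary.

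**Conclusion.** The point holds as an improvement. The planned test is sound, but ANCOVA with baseline On-time does at least as well as a t-test on month-3 hours or on change, apart from the trivial loss when baseline is uninformative. At 30 per arm, 1.46 h and ρ 0.5 it adds 10 to 12 points of power over either. Across ρ 0.3 to 0.7 the gain ranges from about 4 to 27 points over month-3 hours and from about 18 down to 2.5 points over change. At 1.90 h it is only about 2 to 4 points over month-3 hours at SD 2 (ρ 0.3 to 0.5).

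These sizes rest on an assumed ρ, two-sided 5% and the SD reading set out above. The direction does not depend on the particular ρ chosen. A reader should not infer that the Welch test is biased or that its result would be unreliable.

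**What to change.** - **Analysis.** For hypothesis (ii), pre-specify ANCOVA of month-3 On-time (hours) on arm plus baseline On-time, in all randomised patients by assigned arm. Report the adjusted CR − sham difference in hours with its 95% CI. Keep the Welch t-test as a sensitivity analysis and name its variable.
- **Baseline.** Confirm that a pre-treatment On-time diary exists or schedule one. It should come before first stimulation, and before randomisation where possible, with the same instrument as month 3.
- **Reconcile.** State one randomisation day (Day 0 or Day 1) and one On-time instrument (the Hauser diary in the at-home schedule or the wearable electronic diary in the Data collection section).

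**Cost.** One degree of freedom and SAP wording. If no baseline diary is already planned, add one schedule line. With randomisation on Day 1, it fits in the 1 to 2 weeks after Day 0. With randomisation on Day 0, the diary would fall after randomisation but before first stimulation, or the order of visits would have to change.
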